2.1.4 Safety endpoints

The safety analysis will be based on the reported adverse events and other safety information, such as clinical laboratory data, vital signs, ECG and physical examination.

Observation period

The observation period will be divided into 4 epochs:

- The **screening** epoch is defined as the time from the signed informed consent date up to the time prior to first administration of the IMP.
- The **treatment** epoch is defined as the time from the first administration of the IMP to the last administration of the IMP + 14 days or until rollover to the LTS12551 study.
- The **residual treatment** epoch is defined as the time from the last administration of the IMP +15 days to the last administration of the IMP + 98 days or until rollover to the LTS12551 study.
- The treatment-emergent adverse event period will include both **treatment** and **residual treatment** epochs.
- The **posttreatment** epoch is defined as the period of time starting the day after the end of the treatment-emergent adverse event period up to the end of the study (defined as last protocol planned visit or the resolution/stabilization of all serious adverse events and adverse events with pre-specified monitoring).

The on-study observation period is defined as the time from start of treatment until the end of the study (defined as last protocol planned visit or lost to follow-up or the resolution/stabilization of all serious adverse events and adverse events with pre-specified monitoring).

2.1.4.1 Adverse events variables

Adverse event observation period

- Pretreatment adverse events are adverse events that developed or worsened or became serious from the signed informed consent date up to first administration of IMP
- Treatment-emergent adverse events are adverse events that developed or worsened or became serious during the treatment-emergent adverse event period
- Posttreatment adverse events are adverse events that developed or worsened or became serious during the posttreatment period

All adverse events (including serious adverse events and adverse events with pre-specified monitoring/of special interests) will be coded to a lower-level term (LLT), preferred term (PT), high-level term (HLT), high-level group term (HLGT), and associated primary system organ class (SOC) using the version of Medical Dictionary for Regulatory Activities (MedDRA) currently in effect at Sanofi at the time of database lock.

Adverse events of special interest (AESI) and other selected AE groupings will be searched based on the criteria in [Table 3](#):

Table 3 - Criteria for adverse events of special interest and other selected AE groupings

AE Grouping	Criteria
AESI	
Anaphylactic reaction	Anaphylactic reaction algorithmic approach (Introductory Guide for Standardised MedDRA Queries (SMQs) Version 18.1): includes anaphylactic reaction narrow SMQ (20000021) terms; for selection based on occurrence of multiple events, the events must have occurred within 24 hours of each other
Hypersensitivity (medically reviewed)	SMQ hypersensitivity (20000214) narrow search and [AE corrective treatment/therapy='Y' or Action taken with IMP='Drug withdrawn' or Action taken with IMP='Drug interrupted'] followed by blinded medical review (documented process) for selection of relevant events
Serious injection site reactions or severe injection site reactions that last longer than 24 hours	HLT = 'Injection site reaction' and either with serious status, or with severe status and (AE end date/time - AE start date/time) ≥ 24 hours or ongoing
Severe or serious infection	Primary SOC = 'Infections and infestations' and with severe or serious status
Parasitic infection	Infection Type 'Parasitic' checked on eCRF Infection Defined as AESI Complementary Form
Opportunistic infection	Infection Type 'Opportunistic' checked on eCRF Infection Defined as AESI Complementary Form
Drug-related hepatic disorder	Drug-related hepatic disorders-Comprehensive search narrow SMQ (20000006)

AE Grouping	Criteria
Pregnancy	Primary SOC = 'Pregnancy, puerperium and perinatal conditions' or PT in (Aborted pregnancy, False negative pregnancy test, Pregnancy test positive, Pregnancy test urine positive, Ectopic pregnancy termination)
Symptomatic overdose with IMP	Is the event a Symptomatic Overdose with IMP? is answered Yes on AE eCRF.
Symptomatic overdose with non-IMP	Is the event a Symptomatic Overdose with non-IMP? is answered Yes on AE eCRF
Other selected AE grouping	
Injection site reaction	HLT = 'Injection site reaction'
Malignancy	Sub-SMQ (20000091)– Malignant or unspecified tumors
Suicidal behavior	PT in (Completed suicide, Suicidal ideation, Depression suicidal, Suicidal behavior, Suicide attempt)
Partner pregnancy	PT in (Pregnancy of partner, Miscarriage of partner)
Conjunctivitis (narrow)	PT in (Conjunctivitis, Conjunctivitis allergic, Conjunctivitis bacterial, Conjunctivitis viral, Atopic keratoconjunctivitis)
Conjunctivitis (broad)	PT in (Conjunctivitis, Conjunctivitis allergic, Conjunctivitis bacterial, Conjunctivitis viral, Atopic keratoconjunctivitis, Blepharitis, Dry eye, Eye irritation, Eye pruritus, Lacrimation increased, Eye discharge, Foreign body sensation in eyes, Photophobia, Xerophthalmia, Ocular hyperaemia, Conjunctival hyperaemia)
Hypereosinophilia	HLT = 'Eosinophilic disorders' or PT = 'Eosinophil count increased'

In addition, AESIs reported by the investigator in CRF will be summarized separately.

2.1.4.2 Deaths

The deaths observation period are per the observation periods defined above.

- Death on-study: deaths occurring during the on-study observation period
- Death on-treatment: deaths occurring during the treatment-emergent adverse event period
- Death poststudy: deaths occurring after the end of the study

2.1.4.3 Laboratory safety variables

Clinical laboratory data consists of blood analysis, including hematology, clinical chemistry, and urinalysis. Clinical laboratory values after conversion will be analyzed in standard international units and international units will be used in listings and tables. The same set of analysis will also be prepared in US units.

Blood samples for clinical laboratories will be taken at Visit 1(Week -4±1), Visit 2 (Week 0), Visit 4 (Week 4), Visit 6 (Week 8), Visit 8 (Week 12), Visit 9 (Week 16), Visit 10 (Week 20), Visit 11 (Week 24), Visit 12 (Week 28), Visit 13 (Week 32), Visit 14 (Week 36), Visit 15 (Week 40), Visit 16(Week 44), Visit 17(Week 48), Visit 18(Week 52), Visit 19(Week 56), Visit 20(Week 60), Visit 21(Week 64) and early termination unless otherwise specified. The laboratory parameters will be classified as follows:

- Hematology
 - **Red blood cells and platelets and coagulation:** hemoglobin, hematocrit, red blood cell count, platelet count
 - **White blood cells:** white blood cell count, neutrophils, lymphocytes, monocytes, basophils, eosinophils
- Clinical chemistry
 - **Metabolism:** glucose, total cholesterol, total protein, creatine phosphokinase
 - **Electrolytes:** sodium, potassium, chloride, bicarbonate
 - **Renal function:** creatinine, blood urea nitrogen, uric acid
 - **Liver function:** alanine aminotransferase, aspartate aminotransferase, alkaline phosphatase, lactate dehydrogenase, total bilirubin (in case of values above the normal range, differentiation in conjugated and non-conjugated bilirubin), albumin
 - **Pregnancy test:** serum β -human chorionic gonadotropin (all female patients) will be performed at screening (Visit 1) in women of childbearing potential
 - **Hepatitis screen:** clinical laboratory testing at Visit 1 and Visit 17 (only applicable for patients planned to participate in the OLE study) add hepatitis screen including hepatitis B surface antigen (HBs Ag), hepatitis B Surface antibody (HBs Ab), hepatitis B core antibody (HBc Ab), hepatitis C virus antibodies (HCV Ab), In case of results showing HBs Ag (negative), HBs Ab (negative) and HBc Ab (positive), an HBV DNA testing may be performed prior to randomization to rule out a false positivity if the investigator believes the patient is a false positive, or to clarify the serological status if the investigator finds it unclear to interpret in absence of known HBV infection. In case of results showing HCV Ab (positive), an HCV RNA testing may be performed to rule out a false positivity, if the investigator believes the patient is a false positive.
 - **Hepatitis B viral load** will be tested at Visit 2, then every 12 weeks until Visit 14 and end of treatment period for patients in Japan or other countries/regions if there is local regulatory requirement who are HBs Ag negative and HBs Ab positive at screening.
 - **HIV screen:** anti-HIV-1 and HIV-2 antibodies will be tested at Visit 1 and Visit 17 (only applicable for patients planned to participate in the OLE study)
 - **Anti-nuclear antibody (ANA)** will be tested at Visit 1 and Visit 17 (only applicable for patients planned to participate in the OLE study)

Note: Anti-ds DNA antibody will be tested if ANA is positive ($\geq 1:160$ titer).

- Serum immunoglobulins (limited to Visit 1(Week -4±1), Visit 8 (Week 12), Visit 11 (Week 24), Visit 14 (Week 36), Visit 18(Week 52), and Visit 21 (Week 64)): quantitative immunoassays for total IgG, IgG subclasses 1-4, IgM, and IgA.

Urine samples will be collected as follows:

- **Urinalysis** (limited to Visit 1(Week -4±1), Visit 8 (Week 12), Visit 11 (Week 24), Visit 14 (Week 36), Visit 18(Week 52), and Visit 21 (Week 64)): Urine dipstick analysis specific gravity, pH, glucose, ketones, blood, protein, nitrate, leukocyte esterase, urobilinogen and bilirubin (by dipstick). If any parameter on the dipstick is abnormal, a urine sample should be sent to the central laboratory for testing. If positive for proteins, microscopic analysis is performed by central laboratory.
- A **urine dipstick pregnancy test** will be performed at Visit 2 prior to randomization and Visit 4 (Week 4), Visit 6 (Week 8), Visit 8 (Week 12), Visit 9 (Week 16), Visit 10 (Week 20), Visit 11 (Week 24), Visit 12 (Week 28), Visit 13 (Week 32), Visit 14 (Week 36), Visit 15 (Week 40), Visit 16(Week 44), Visit 17(Week 48), Visit 18(Week 52), Visit 21(Week 64)

Technical formulas are described in [Section 2.5.1](#).

2.1.4.4 Vital signs variables

Vital signs include: including blood pressure (mmHg), heart rate (beats per minute), respiratory rate (breaths per minute), body temperature (degrees Celsius) and body weight (kg) will be measured at the screening and randomization visits (Visits 1 and 2) and every subsequent visit. Height (cm) will be measured at screening (Visit 1) for all patients and will be measured throughout the study for adolescent patients. Vital signs will be measured in the sitting position using the same arm at each visit, and will be measured prior to receiving investigational product at the clinic visits.

2.1.4.5 Electrocardiogram variables

One recording of a standard 12-lead ECG will be performed centrally at Visit 1(Week -4±1), Visit 3 (Week 2), Visit 4 (Week 4), Visit 8 (Week 12), Visit 11 (Week 24), Visit 14 (Week 36), Visit 18(Week 52), and Visit 21 (Week 64). At the post-randomization visits, ECGs will be performed prior to investigational product administration. A minimum of 3 complexes in an appropriate lead (lead II) will be averaged to determine the PR-interval, QT/QTc-interval, QRS-complex and heart rate will be measured for each ECG. All ECG recordings will be centrally read by independent experts.

2.1.4.6 Physical Examination

Physical examinations will be performed at Visit 1(Week -4±1), Visit 11 (Week 24), Visit 18(Week 52), and Visit 21 (Week 64) including an assessment of general appearance, skin, eyes, ear/nose/throat, heart, chest, abdomen, reflexes, lymph nodes, spine, and extremities. All deviations from normal will be recorded, including those attributable to the patient's disease.

Refer to Section 1.2 Study Flow Chart for the schedule of physical examination performed throughout this study.

2.1.5 Pharmacokinetic variables

Predose serum dupilumab concentrations at Visit 2 (Day 1), dupilumab trough levels at Week 2, Week 4, Week 8, Week 12, Week 16, Week 24, Week 36, Week 52 and follow-up serum dupilumab at Week 56, Week 60, Week 64 will be provided.

2.1.6 Anti-drug antibody (ADA) variables

Anti-dupilumab antibody (ADA) status (negative or titer value, if positive in the ADA assay) at Visit 2 (Day 1), Week 12, Week 24, Week 52 and follow up at Week 64 will be provided. Patients who discontinue early from treatment or patients who choose not to participate in the OLE study visit may be asked to return to the clinic to have additional ADA samples collected for analysis based on the overall clinical presentation at that time.

Status in the ADA assay will be classified as the following:

1. Pre-existing immunoreactivity is defined as:

An ADA positive response in the assay at baseline with all post treatment ADA results negative, OR an ADA positive response at baseline with all post treatment ADA responses less than 4-fold over baseline titer levels.

2. Treatment-emergent response is defined as:

An ADA positive response in the assay post first dose, when baseline results are negative or missing.

3. Treatment-emergent ADA responses are further classified as Persistent, Indeterminate or Transient

- a) Persistent Response - defined as a treatment-emergent ADA response with two or more consecutive ADA positive sampling time points, separated by greater than (>) 12-week period (84 days), with no ADA negative samples in between.

- b) Indeterminate Response - defined as a treatment-emergent response with only the last collected sample positive in the ADA assay

- c) Transient Response - defined as a treatment-emergent response that is not considered persistent OR indeterminate

4. Treatment-boosted response is defined as:

An ADA positive response in the assay post first dose that is greater-than or equal to 4-fold over baseline titer levels, when baseline results are positive.

Titer values (Titer value category)

- Low (Titer < 1000)
- Moderate ($1,000 \leq \text{Titer} \leq 10,000$)

- High (Titer > 10,000)

ADA positive samples will be further characterized for presence of neutralizing antibody response in the NAb assay.

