Archival serum l	x																																																					
EQ-5D-5L	x																																																					
HADS m	x																																																					
SNOT-22 n	x																																																					
RQLQ(S) +12 o	x																																																					
Vaccine IgG p	x																																																					

- a** Patients who permanently discontinue treatment early will continue the remaining visits per protocol schedule with a +/-5 day window until end of study. At the time of permanent treatment discontinuation, patients will perform early treatment discontinuation (ETD) visit with all the assessments defined for Visit 18 (EOT). Visit 19 (Week 56) and Visit 20 (Week 60) will not be performed.
- b** Forced expiratory volume (FEV1), PEF, Forced vital capacity (FVC), Forced expiratory flow between 25% to 75% of vital capacity (FEF25%-75%) at all visits; pulmonary function tests should be performed in the morning if possible, but if it could only be done at a different time of the day, the spirometry should be done at approximately the same time of the day at each visit throughout the study. Spirometry will be performed after a wash out period of bronchodilators according to their action duration, for example, withholding the last dose of salbutamol/albuterol or levosalbutamol/levalbuterol for at least 6 hours and withholding the last dose of LABA for at least 12 hours (ultra-long acting LABA like vilanterol should be withheld for at least 24 hours) and withholding the last dose of Long-Acting Muscarinic Antagonist (LAMA) for at least 24 hrs. This will be verified before performing the measurements.
- c** Electronic diary/PEF meter is used for daily recording of salbutamol/albuterol or levosalbutamol/levalbuterol use, asthma controller drug use, oral steroid requirements, nocturnal awakenings due to asthma symptoms, morning and evening asthma symptom NRS scores and AM and PM PEF. This device is dispensed at Visit 1 and information is downloaded from this device on the other indicated days.

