### **9.3 OTHER ENDPOINTS**

#### **9.3.1 Systemic drug concentration and anti-drug antibodies**

##### **9.3.1.1 Sampling time**

Serum samples for determination of functional dupilumab and anti-dupilumab antibodies (also known as anti-drug antibodies (ADA)) will be collected as per study flow chart (see Section 1.2 and Section 1.3). The date of collection should be recorded in the patient e-CRF. The date and time also will be collected on the central laboratory requisition form and entered into the database through data transfers from the central laboratory. Patients who discontinue early from treatment or patients who choose not to participate in the long term extension study may be asked to return to the clinic to have additional ADA samples collected for analysis based on the overall

assessment of antibody titers and/or clinical presentation at the time of discontinuation or at the time of last study visit.

In the event of any SAE or any AESI of anaphylactic reactions or systemic allergic reactions that are related to IMP and require treatment, or severe injection site reaction lasting longer than 24 hours, samples will be collected near the onset and resolution of the event for any additional analysis if required or for archival purposes. An unscheduled systemic drug concentration page in the e-CRF must be completed as well.

Pre-existing anti-drug antibodies are defined as:

- An ADA positive response in the assay at baseline with all post treatment ADA results negative, OR
- An ADA positive response at baseline with all post treatment ADA responses less than 4-fold over baseline titer levels.

Treatment-emergent anti-drug antibodies are defined as:

- An ADA positive response in the assay post first dose, when baseline results are negative or missing.

Treatment-boosted anti-drug antibodies are defined as:

- An ADA positive response in the assay post first dose that is greater-than or equal to 4-fold over baseline titer levels, when baseline results are positive.

Treatment-emergent (TE) ADA responses are further classified as Transient, Persistent or Indeterminate

- a) Persistent Response- defined as a treatment-emergent response with two or more consecutive ADA positive sampling time points, separated by more than 12-week period (with no ADA negative samples in between).
- b) Indeterminate Response- defined as a treatment-emergent response with only the last collected sample positive in the ADA assay

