## 10 STUDY PROCEDURES

### 10.1 VISIT SCHEDULE

The clinical trial consists of three periods, using an add-on therapy approach to inhaled corticosteroid in combination with one or two other controller medications:

- Screening Period (4±1 weeks; Visit 1)
- Randomized Treatment Period ( 52 weeks; Visits 2-18)
- Post-treatment Period (12 weeks; Visits 19-21)

The study visits occur on the planned dates (relative to the first injection), as scheduled. The visit schedule should be adhered to within the ± 3 day visit window.

All the study visits should be scheduled in the morning, to have the spirometry performed and the patient should be fasting for serum chemistry tests. However, if the visit can only be done at a different time of the day and the patient is not fasting, then he/she should be advised to have a light meal and the site should document that serum chemistry was not obtained under fasting conditions. For spirometry, it should be performed at approximately the same time of the day at each visit throughout the study.

Patients who permanently discontinue the study medication will be asked and encouraged to return to the clinic for study visits and participate in assessments according to the visit schedule until the end of the study with a +/-5 day window (See Section 1.3). Under exceptional circumstances when a patient cannot come to the site for the scheduled visit, a phone contact can be made after sponsor approval is given. During the phone contact, at least information about AEs, concomitant medication and asthma exacerbation events should be collected.

Patients who discontinue early from treatment or patients who choose not to participate in the OLE study may be asked to return to the clinic to have additional ADA samples collected for analysis based on the overall assessment of antibody titers and/or clinical presentation at the time of discontinuation or at the time of last study visit.

Reminder: sexually active female patients of reproductive potential are required to practice an effective contraception throughout the participation in the study including a 12-week period after last IMP dose. Sites should counsel these patients, with special attention towards adolescent patients regarding the importance of practicing responsible and effective contraception throughout the participation in the study including a 12-week period after last IMP dose.

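### Persistent ADA requires positives more than 84 days apart, but two of the three planned post-dose sampling gaps are exactly 84 days and the date basis is not stated

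*SAP*

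**What the plan says.** SAP 2.1.6 divides treatment-emergent ADA responses into three classes.

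- **Persistent:** two or more consecutive positive sampling time points "separated by greater than (>) 12-week period (84 days), with no ADA negative samples in between". Protocol 9.3.1.1 has the same strict rule without the day count: "separated by more than 12-week period (with no ADA negative samples in between").
- **Indeterminate:** "defined as a treatment-emergent response with only the last collected sample positive in the ADA assay".
- **Transient:** "defined as a treatment-emergent response that is not considered persistent OR indeterminate".

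The same SAP section plans ADA status at Day 1 and then at "Week 12, Week 24, Week 52 and follow up at Week 64 will be provided". Patients who enter the open-label extension skip the post-treatment period (Protocol, Clinical Trial Summary), so they have no Week 64 sample. Patients who stop treatment early have one further scheduled ADA sample at the early treatment discontinuation (ETD) visit (Protocol 1.3).

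Protocol 10.1 allows ±3 days for scheduled visits ("The visit schedule should be adhered to within the ± 3 day visit window") and ±5 days after permanent discontinuation ("until the end of the study with a +/-5 day window"). Protocol 9.3.1.1 has the collection date recorded, but no text in either document links that date, the nominal visit or the SAP Table 10 windows to the persistence rule.

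**The concern.** The threshold and the sampling schedule do not fit each other. A strict limit of 84 days is applied to a schedule in which two of the three post-dose gaps are planned at exactly 84 days, and the basis for measuring the gap is left open.

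Both main ways of applying the rule give odd results. On nominal visits, sustained positivity over 12 weeks at either end of the schedule is excluded by construction. On actual dates, two patients with identical serology can receive different labels because one came a day late.

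The order of the categories makes this worse at the end of the study. A patient positive only at Week 64 is indeterminate. A patient positive at both Weeks 52 and 64 no longer fits that class and falls through to transient, a label that suggests resolution, although no negative sample followed.

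What is at stake is the meaning of the persistent and transient counts. ADA incidence is a secondary objective (Protocol 5.2), and these counts are planned outputs (Protocol 11.4.4.2; SAP 2.4.6.1.2).

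**Working it through.** **Inputs**

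- Threshold: 12 × 7 = 84 days, which reproduces the figure in SAP 2.1.6.
- Target days (SAP 2.5.4, Table 10), equal to 7 × week + 1: Week 12 = 85, Week 24 = 169, Week 52 = 365, Week 64 = 449.
- A treatment-emergent response needs a negative or missing baseline (SAP 2.1.6), so Day 1 cannot be part of a positive run. Only the post-dose gaps matter.
- Visit windows of ±3 and ±5 days (Protocol 10.1).

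**Step 1: planned gaps**

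- Weeks 12 to 24: 169 − 85 = 84, not more than 84
- Weeks 24 to 52: 365 − 169 = 196, more than 84
- Weeks 52 to 64: 449 − 365 = 84, not more than 84

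**Step 2: labels on nominal visits**

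Write results in the order Weeks 12, 24, 52, 64. There are 2⁴ − 1 = 15 patterns with at least one positive.

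| Group | Patterns | Number | Label at >84 | Label at ≥84 |
|---|---|---|---|---|
| Positive at both Weeks 24 and 52 | `-++-` `-+++` `+++-` `++++` | 4 | persistent | persistent |
| Only consecutive positives are Weeks 12–24 or 52–64 | `++--` `++-+` `--++` `+-++` | 4 | transient | persistent |
| Only Week 64 positive | `---+` | 1 | indeterminate | indeterminate |
| No consecutive positives, other | `+---` `-+--` `--+-` `-+-+` `+--+` `+-+-` | 6 | transient | transient |

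So 4 of 15 labels turn on the equality. For extension entrants (Weeks 12, 24, 52) there are 2³ − 1 = 7 patterns, and one, `++-`, turns on it. These are logically possible patterns, not patients; the documents give no ADA incidence.

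**Step 3: labels on actual dates**

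For a boundary pair, gap = 84 + (second deviation − first deviation).

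- Both visits ±3: range 78 to 90 days
- Both visits ±5: range 74 to 94 days
- The 196-day gap is never below 196 − 10 = 186 days, so it always qualifies.

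For illustration, assume independent, uniform whole-day deviations. This is an assumption; the documents say nothing about it. By symmetry the pairs above 84 are half of those not equal to 84:

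- ±3 and ±3: (49 − 7)/2 = 21, and 21/49 = 43%
- ±3 and ±5: (77 − 7)/2 = 35, and 35/77 = 45%
- ±5 and ±5: (121 − 11)/2 = 55, and 55/121 = 45%

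If every visit falls on its target day, the figure is 0%.

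**Step 4: Table 10 windows as a third basis**

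Table 10 assigns ADA samples on days 1–126 to Week 12 and on days 127–266 to Week 24. Samples on days 85 and 127 would then count as Weeks 12 and 24 although 127 − 85 = 42 days apart. SAP 2.5.4 gives these windows for by-visit descriptive summaries only, so they should not carry the rule.

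**The case against.** The strongest reply is that actual dates are the natural reading. The SAP adds a day count to the protocol's weeks, collection dates are recorded, and the strict inequality stands in both documents. On that reading the rule is computable, and every cut-off must separate neighbouring values.

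Part of this stands. The protocol and SAP do not contradict each other, and the result that no boundary pair can qualify belongs to the nominal reading. But the rule speaks of sampling time points, which leaves nominal visits open, and the SAP never settles it. A cut-off placed exactly on two planned intervals also differs from an arbitrary cut-off, because ordinary scheduling noise then decides the label.

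The objection that this is only descriptive also stands. The ADA–PK and ADA–efficacy associations that name these classes are optional, and the classes are not among the variables named for the ADA–safety associations (SAP 2.4.6.1.2). Protocol 11.4.4.2 also plans a listing of titers, so the serology stays visible.

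Two stronger inferences should be resisted.

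- **The 43–45% as an expected misclassification rate.** It rests on independent uniform drift. Sites book each visit from the current one (Protocol 10.1.8 to 10.1.12), so deviations may be correlated.
- **A count of affected patterns for patients with an ETD sample.** The documents do not say whether separation runs from the first to the last positive of a run or between adjacent positives. Positives on days 85, 169 and ETD day 211 span 126 days from first to last, but the adjacent gaps are 84 and 42. The counts of 4 of 15 and 1 of 7 hold on both readings; an ETD count would not.

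**Conclusion.** The point holds as a minor correction. Two of the three planned post-dose gaps equal the threshold exactly, and the date basis is unstated. On nominal visits, 4 of 15 patterns (1 of 7 without Week 64) can never be persistent, including a response positive at Weeks 52 and 64 and never seen to clear. On actual dates, drift within the permitted windows decides those labels. The arithmetic on the four scheduled samples needs no assumption beyond the planned days; only the 43–45% illustration does.

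A reader might infer that the ADA results as a whole, or the efficacy conclusions, are in doubt. The documents do not support that. Total treatment-emergent, treatment-boosted and pre-existing ADA counts do not use this rule, and none of the tests in SAP Table 6 depends on it. The effect stops at the persistent/transient split, the peak-titer summaries by class and any exploratory association that uses the class.

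**What to change.** In SAP 2.1.6, before database lock:

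- Define persistent as a run of two or more consecutive ADA-positive samples, with no negative sample in between, whose first and last positives are at least 12 weeks apart. This also settles the first-to-last question.
- Judge the separation by nominal visit when both samples are scheduled samples taken within their protocol visit window.
- Otherwise judge it by actual collection date, at least 84 days. This covers ETD, recall, unscheduled and out-of-window samples.
- State that the Table 10 windows are not used for this rule.
- Leave the indeterminate and transient definitions unchanged.
- Record in SAP 1.6 that the at-least rule departs from the protocol's strict inequality.

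The cost is a few lines of SAP text and programming, using dates already collected. Persistent counts may rise slightly and transient counts fall. A small unevenness remains: an in-window scheduled pair can be as close as 78 days (74 with ±5 windows) and still qualify, while a pair judged on actual dates needs 84. That is acceptable for a descriptive label and preferable to leaving the choice until results are visible.
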